### Women of childbearing potential

WOCBP are defined as all women physiologically capable of becoming pregnant, including women whose career, lifestyle, or sexual orientation precludes intercourse with a male partner and women whose partner have been sterilized by vasectomy or other means.

### Women of non-childbearing potential

Women are considered post-menopausal and not of childbearing potential if they have had 12 months of natural (spontaneous) amenorrhea with an appropriate clinical profile (i.e. age appropriate history of vasomotor symptoms) or have had surgical bilateral oophorectomy (with or without hysterectomy), total hysterectomy or bilateral tubal ligation at least six weeks prior to screening. In the case of oophorectomy alone, only when the reproductive status of the woman has been confirmed by follow up hormone level assessment is she considered not of childbearing potential.

### Highly effective contraception methods include:

- Total abstinence (when this is in line with the preferred and usual lifestyle of the subject. Periodic abstinence (e.g. calendar, ovulation, symptothermal, post-ovulation methods) and withdrawal are not acceptable methods of contraception
- Male/female sterilization
- Use of oral, injected or implanted hormonal methods of contraception or placement of an intrauterine device (IUD) or intrauterine system (IUS) or other forms of hormonal contraception that have comparable efficacy (failure rate <1%), for example hormone vaginal ring or transdermal hormone contraception

In case of use of oral contraception, women should be stable on the same pill for a minimum of 3 months before taking investigational drug.

- 22. Other history or current diagnosis of ECG abnormalities not due to cardiac sarcoidosis at screening as determined by the investigator and based on the totality of the safety information to indicate significant safety risk. The following should be considered by the investigator in guiding the determination as part of the overall assessment, but should not be considered in isolation:
  - PR > 200 msec
  - QRS complex > 120 msec
  - QTcF > 450 msec (males)
  - QTcF > 460 msec (females)
- 23. Concomitant clinically significant cardiac arrhythmias, e.g. sustained ventricular tachycardia, and clinically significant second or third degree AV block without a pacemaker
- 24. Significant illness which has not resolved within two weeks prior to initial dosing
- 25. Donation or loss of 400 mL or more of blood within eight weeks prior to initial dosing, or longer if required by local regulation
- 26. Any surgical or medical condition which might significantly alter the absorption, distribution, metabolism, or excretion of drugs, or which may jeopardize the subject in case of participation in the study. The investigator should make this determination in consultation with the sponsor and in consideration of the subject's medical history and/or clinical or laboratory evidence.
- 27. Clinical Status Determination (CSD) of "deteriorating" at Day-28 (V102) or Day 1 (V201)

- 28. A diagnosis of Lofgren's syndrome
- 29. History of pancreatitis
- 30. Other pulmonary disease (i.e., asthma, bronchiectasis, COPD, etc.) unrelated to sarcoid as determined by the investigator
- 31. Active drug or alcohol abuse (as defined by the investigator) within 3 months prior to screening.

# 5 **Restrictions for Study Subjects**

For the duration of the study, the subjects should be informed and reminded of the restrictions outlined in this section.

## 5.1 Contraception requirements

Women of childbearing potential must be informed that taking the study treatment may involve unknown risks to the fetus if pregnancy were to occur during the study, and agree that in order to participate in the study they must adhere to the contraception requirement outlined in Section 4.2 (Exclusion Criteria). If there is any question that the subject will not reliably comply, they should not be entered or continue in the study.

# 5.2 Prohibited treatment

Use of the following treatments are NOT allowed in the timeframes reported in Table 5-1.

Commercially Confidential Information

# 5.3 Dietary restrictions and smoking

Use of any inhaled substance, including but not limited to tobacco or marijuana products or use of any electronic cigarette or vaping device is not allowed during the study. Respiratory inhalers or nebulizers for delivery of prescribed medication for pulmonary sarcoidosis are allowed.

Patients will be asked to not eat or drink anything (except water) for 8 hours before completing the chemistry and fasting lipid panel assessment at each applicable visit.

# 5.4 Other restrictions

No strenuous physical exercise is allowed within 30 minutes of Spirometry and DLCO assessments.

# 6 Treatment

# 6.1 Study treatment

Details on the requirements for storage and management of study treatment, and instructions to be followed for subject numbering, prescribing/dispensing and taking study treatment are outlined in the Pharmacy Manual.

## 6.1.1 Investigational treatment and control drug(s)

### Table 6-1Overview of study medication

Study Drug	Formulation	Appearance	Unit dose	Packaging	Provided by
CMK389	Powder for Solution for Infusion	a white to off- white Iyophilisate	150 mg powder in a 6 mL glass vial	open label bulk	Novartis

## 6.1.2 Bio-batch retention samples

Not applicable

## 6.1.3 Additional study treatment

No additional treatment beyond investigational drug and placebo control drug are included in this trial.

Pre-medication (prior to infusion of CMK389) with corticosteroids, NSAIDs and paracetamol is not allowed.

Note: in the event of hypersensitivity reaction, refer to Section 6.9.

# 6.2 Treatment arms

Subjects will be assigned to one of the following 2 treatment arms in a ratio of 1:1.

Study treatments are defined as:

- four doses of CMK389 10 mg/kg i.v. (one dose q4 weeks)
- four doses of matching placebo i.v. (one dose q4 weeks)

# 6.3 Treatment assignment and randomization

Randomized treatment will be assigned to individual subjects by way of a randomization number, which will be in the range of 5101-5200, 5201-5300, for the 2 strata (azathioprine or methotrexate), respectively.

The randomization number is only used to identify which treatment the subjects have been randomized to receive. The Subject number assigned to a subject at screening remains the unique identifier for the subject throughout the study. For information on subject numbering, please see 'Subject numbering' section in the SOM.

The randomization numbers will be generated using the following procedure to ensure that treatment assignment is unbiased and concealed from subjects and investigator staff. A randomization list will be produced by the NIRT provider using a validated system that automates the random assignment of subject numbers to randomization numbers. These randomization numbers are linked to the different treatment arms.

Randomization will be stratified by prior sarcoidosis immunosuppressant therapy (azathioprine or methotrexate).

The randomization scheme for subjects will be reviewed and approved by a member of the Randomization Office.

Follow the details outlined in the SOM regarding the process and timing of treatment assignment and randomization of subjects.

# 6.4 Treatment blinding

This is a subject and investigator blinded study. Subjects and investigators will remain blinded to study treatment throughout the study, except where indicated below.

The identity of the treatments will be concealed by the use of study drugs that are all identical in packaging, labeling, schedule of administration, appearance, and odor.

### Site staff

With the exception of an unblinded pharmacist, all site staff (including study investigator and study nurse) will be blinded to study treatment throughout the study. See Section 7.2 for details on early discontinuation. For detailed information about the scheduled unblinding of subjects, please refer to the SOM.

Unblinding a single subject at site for safety reasons (necessary for subject management) will occur via an emergency system in place at the site (see Section 6.7).

Drug product will be supplied as open label bulk so an unblinded pharmacist who is independent of the study team will be required in order to maintain the blind. This unblinded pharmacist will receive the treatment allocation from the NIRT system. Appropriate measures must be taken by the unblinded pharmacist to ensure that the treatment assignments are concealed from the rest of the site staff.

### Sponsor staff or delegate

The following unblinded sponsor roles are required for this study:

Unblinded clinical staff managing drug re-supply to site

Unblinded sample analyst(s) (PK, CCI )

Commercially Confidential Information

The sample analysts will receive a copy of the randomization schedule (via request to the Randomization Office), to facilitate analysis of the samples. The sample analysts will provide the sample data to the study team under blinded conditions unless otherwise allowed.

The study statistician will be able to access the randomization list for interim analyses and is allowed to share unblinded information with the rest of the clinical trial team (CTT) as appropriate for internal decision purposes, as outlined in Table 6-2. For example, unblinded summaries and unblinded individual data can be shared with the team for interim analyses.

Study programmers and other personnel involved in study data analysis CCI are allowed to access treatment assignment information for the purpose of conducting interim analyses.

The CTT is allowed to share unblinded results with other sponsor staff (e.g. decision boards) as required for internal decision making on the study or the project at the time of interim analyses while the study is ongoing.

All unblinded personnel will otherwise keep randomization lists and data or information that could unblind other study team members confidential and secure except as described above.

Following final database lock all roles may be considered unblinded.

Role		Time or E	vent	
	Randomization list generated	Treatment allocation & dosing	Safety event (single subject unblinded)	
Subjects/Patients	В	В	UI	
Site staff	В	В	UI	
Unblinded site staff (see text for details)	В	UI	UI	
Drug Supply and Randomization Office	UI	UI	UI	CCI
Unblinded sponsor staff (see text for details)	В	UI	UI	
Statistician/statistical programmer/data analysts	В	В	UI	
All other sponsor staff not identified above	В	В	UI	

### Table 6-2 Blinding levels

B Remains blinded

UI Allowed to be unblinded on individual patient level

# 6.5 Treating the subject

CMK389 will be administered to the subject via i.v. infusion for approximately one hour at the study site. See the pharmacy manual for further details.

Sponsor qualified medical personnel will be readily available to advise on trial related medical questions or problems.

# 6.6 Permitted dose adjustments and interruptions of study treatment

Study treatment dose adjustments and/or missed doses are not permitted.

For instructions regarding infusion interruptions, refer to the Pharmacy Manual.

## 6.7 Emergency breaking of assigned treatment code

Emergency code breaks must only be undertaken when knowledge of the assigned treatment is required to in order to treat the subject safely. Most often, study treatment discontinuation and knowledge of the possible treatment assignments are sufficient to treat a study subject who presents with an emergency condition. Emergency treatment code breaks are performed using the NIRT. When the investigator contacts the system to break a treatment code for a subject, he/she must provide the requested subject identifying information and confirm the necessity to break the treatment code for the subject. The investigator will then receive details of the investigational drug treatment for the specified subject and a fax or email confirming this information. The system will automatically inform the study monitor for the site and the Study Team that the code has been broken.

It is the investigator's responsibility to ensure that there is a dependable procedure in place to allow access to the NIRT at any time in case of emergency. The investigator will need to provide:

- protocol number
- study drug name (if available)
- subject number.

In addition, the investigator must provide oral and written information to inform the subject how to contact his/her backup in cases of emergency when he/she is unavailable to ensure that un-blinding can be performed at any time.

An assessment will be done by the appropriate site personnel and sponsor after an emergency unblinding to assess whether or not study treatment should be discontinued for a given subject and, if applicable, whether the subject can continue with follow up assessments.

## 6.8 Treatment exposure and compliance

Subjects will receive all study medication at the Investigator site. Study medication will be administered by site personnel, compliance will be ensured by appropriate training of site personnel. The date and time of administration of study drug will be recorded in the dosage administration record section of the eCRF.

# 6.9 Recommended treatment of adverse events

Acute infusion or hypersensitivity reactions: Study participants are required to undergo observation for a minimum of two hours post-infusion prior to leaving the site (or longer if deemed necessary by the Investigator). In the event of an acute infusion or hypersensitivity reaction, the investigator should consider the criteria for treatment discontinuation (Section 7.2), and the patient should be treated with antihistamines and glucocorticoids. Depending on severity, patients may also require supplemental oxygen, volume expansion, catecholamines and transfer to an intensive care setting. Plasmapheresis to decrease the systemic concentration of CMK389 may be considered dependent on the patient's condition. Patients should be observed for at least four hours after resolution of signs and symptoms; and those who have experienced severe infusion reactions should be closely observed for 24 hours after resolution because of the risk for a biphasic episode.

**Infections:** In the event of an infection, the investigator should consider the criteria for treatment discontinuation (Section 7.2), as well as consider early treatment with specific antimicrobial therapy on the basis of clinical diagnosis or suspicion thereof (e.g., antiviral treatment for herpes simplex or zoster) in consultation with infectious disease experts, as appropriate.

Medication used to treat AEs must be recorded on the Concomitant medications/Significant non-drug therapies CRF.

## 6.10 **Rescue medication**

Use of rescue medication is not allowed in the context of this study. Therefore, if the investigator believes that continuation of the study is potentially detrimental to a patient's health, such patient should be withdrawn from the study.

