### Treatment Epoch

A 16-week treatment epoch will commence on Day 1. Patients with a CSD of "deteriorating" at this visit will be ineligible to continue in the study. Patients with a CSD of "improved" or "stable" will decrease steroid dose by 1-step. (Note: Steroids will not be tapered below 2.5 mg/day) Then, the patients will be randomized to receive CMK389 or placebo, stratified by prior sarcoidosis immunosuppressant therapy (Stratum 1: azathioprine or Stratum 2: methotrexate).

During the treatment epoch, steroid dose will be guided by the results of CSE/CSD (Figure 3-3). During the treatment epoch, adverse events will be monitored on an ongoing basis. Monthly visits are scheduled to assess safety and efficacy. Physical exam, vital signs, blood draw (safety labs, pharmacokinetic [PK] samples, CCI ), spirometry, 6MWT, mMRC and CCI will be performed during the treatment epoch every 4 weeks or as described in the Assessment Schedule (Table 8-1).

Every effort should be put in place to adhere to this algorithm, but in cases where the Investigator feels that, during the Treatment Epoch, a subject's increase in steroids outside of the specified incremental dose-steps indicated or re-initiation of methotrexate or azathioprine is clinically indicated, this therapy can be started/adjusted. All the actual treatments should be reported in the CRF and all the PD parameters collected after therapy adjustment will be excluded from the primary analysis.

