# 7.2 Discontinuation of study treatment

Subjects may voluntarily discontinue study treatment for any reason at any time.

The investigator must discontinue study treatment for a given subject if, on balance, he/she believes that continuation would be detrimental to the subject's well-being.

Study treatment must be discontinued under the following circumstances:

- Subject is non-compliant with study treatment, as defined by missing any dose
- Subject withdraws consent
- Pregnancy
- Severe infection
- Use of a prohibited treatment as outlined in Table 5-1
- Any situation in which study participation might result in a safety risk to the patient.
- Severe allergic reaction or anaphylaxis, as defined by Sampson criterion #1 (Sampson et al 2006) (Table 7-1), following administration of the study drug
- Any protocol deviation that results in a significant risk to the subject's safety

The appropriate personnel from the site and Novartis will assess whether study treatment should be discontinued for any subject whose treatment code has been broken inadvertently for any reason.

Subjects who discontinue study treatment or who decide they do not wish to participate in the study further should NOT be considered withdrawn from the study UNLESS they withdraw their consent. Where possible, they should return for the assessments indicated for EOS#1 (V399) in the Assessment Schedule (Table 8-1). WOCBP should also complete urine pregnancy tests at home every 4 weeks after the last dose received, for 40 weeks. If they fail to return for these assessments for unknown reasons, every effort (e.g. telephone, email, letter) should be made to contact them.

Table 7-1	Sampson Criterion #1 for diagnosing anaphylaxis
Criteria #1	Acute onset of an illness (minutes to several hours) with involvement of the skin, mucosal tissue, or both (eg, generalized hives, pruritus or flushing, swollen lips-tongue-uvula)
	AND AT LEAST ONE OF THE FOLLOWING
a.	Respiratory compromise (eg, dyspnea, wheeze-bronchospasm, stridor, reduced PEF, hypoxemia)
b.	Reduced BP or associated symptoms of end-organ dysfunction (eg, hypotonia [collapse], syncope, incontinence)

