#### 8.4.2 **Discontinue Sarcoidosis Immunosuppressant Therapy**

During the run-in epoch eligible patients will discontinue methotrexate and azathioprine. The patient's immunosuppressant therapy may be restarted after V299 is completed, at the Investigator's discretion.

Page 63

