### 11.1 Analysis sets

For all analysis sets, subjects will be analyzed according to the study treatment(s) received.

The safety analysis set will include all subjects who received any study drug.

The PK analysis set will include all subjects with at least one available valid (i.e. not flagged for exclusion) PK concentration measurement, who received any study drug and with no protocol deviations with relevant impact on PK data.

The PD analysis set will include all subjects with available PD data and no protocol deviations with relevant impact on PD data. Data collected after a change of the background therapy not

Novartis	Confidential	Page 82
Amended Protocol Version v08 (Clean)		Protocol No. CCMK389X2201

based on the CSE algorithm (see Section 3.1) will be excluded from the analysis set if assessed as having a potentially relevant impact on PD.

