### 11.3 Treatments

Data for study drug administration, rescue medication and concomitant therapies (including steroid dose) will be listed by treatment group and subject.

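### Protocol 6.10 withdraws a patient whom 3.1 would treat off-algorithm and keep, so whether later FVC and steroid increases are recorded can depend on the site

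*Protocol*

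**What the plan says.** **Conduct.**

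- Protocol 6.10: "Use of rescue medication is not allowed in the context of this study". It continues that "if the investigator believes that continuation of the study is potentially detrimental to a patient's health, such patient should be withdrawn from the study".
- Protocol 3.1, Treatment Epoch: where the investigator judges that a steroid increase outside the dose steps or "re-initiation of methotrexate or azathioprine is clinically indicated, this therapy can be started/adjusted". The actual treatments are to be recorded, and data are expected afterwards, because the section says what happens to them.
- Protocol 7.2: patients who stop study treatment, or do not wish to go on, "should NOT be considered withdrawn from the study UNLESS they withdraw their consent". Where possible they return for the EOS#1 (V399) assessments.
- Protocol 8.4.2: "immunosuppressant therapy may be restarted after V299 is completed", at the investigator's discretion. It does not refer to the exception in 3.1.
- Protocol 11.3: "Data for study drug administration, rescue medication and concomitant therapies (including steroid dose) will be listed". SAP 7.1.2 also mentions rescue medication.

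**Data after an off-algorithm change.**

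- Protocol 3.1: "all the PD parameters collected after therapy adjustment will be excluded from the primary analysis", without condition.
- Protocol 11.1: such data "will be excluded from the analysis set if assessed as having a potentially relevant impact on PD". SAP 4 has the same condition.
- SAP 6.1.1: the main analysis drops data after a steroid increase not driven by the algorithm. Case by case, this is at one visit or from a time point onwards. Restart of methotrexate or azathioprine is not named.
- Protocol 11.4.2 and SAP 6.1.5: an optional supplementary analysis uses FVC collected after such changes.
- SAP 6.2.1 to 6.2.3: steroid use and steroid increases count whatever the reason, including the investigator's own decision.

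**The concern.** Take a patient who deteriorates between V202 and V204 and whose investigator wants more treatment than the algorithm gives. A site working from 6.10 would end that patient's participation. A site working from 3.1 would change the therapy, record it and continue the visits. Nothing in the protocol says which section governs.

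An early exit matters because it produces no spirometry. Section 7.2 sends patients who stop treatment to the V399 assessments, and section 8.1 gives those who leave the study early the final-visit assessments. In Table 8-1 spirometry ends at V299. The patients concerned are those doing worst, so whether their later FVC and steroid increases are recorded should not depend on the section a site happens to apply.

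**Working it through.** **1. The plan's own figure.** Inputs from Protocol 11.7: 28 per arm at Week 16, SD 9, true difference 5, criterion of a posterior probability of at least 90%. With uninformative priors this is close to a one-sided 10% test (z = 1.2816).

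- SE = 9 × √(2/28) = 2.405.
- Power = Φ(5/2.405 − 1.2816) = Φ(0.797) = 78.7%, against the stated value of about 80%.
- 66 × 0.85 = 56.1, matching 56 evaluable patients.

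The design figure reproduces.

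**2. What each path delivers.**

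| | Site follows 6.10 (withdrawn) | Site follows 3.1 (kept) |
|---|---|---|
| FVC after the event, to V299 | None | Collected at remaining visits |
| Primary analysis, rule in Protocol 3.1 | Earlier visits only | Earlier visits only |
| Primary analysis, rule in Protocol 11.1 and SAP 4 | Earlier visits only | Later values stay unless judged relevant |
| Primary analysis, rule in SAP 6.1.1 | Earlier visits only | Steroid increase: dropped for one visit or onwards. Methotrexate or azathioprine restart: not named |
| Supplementary analysis | No value | Value available |
| Any-reason steroid endpoints | Off-algorithm increase not counted | Increase counted |

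**3. Under the rule in 3.1 the primary analysis does not separate the paths.** Either way the Week 16 value is absent and is handled as missing at random (MAR). Suppose, as an assumption, that such events come on top of the 15% dropout, equally in both arms. Power = Φ(5/(9 × √(2/n)) − 1.2816):

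- 5% extra, n = 26.6: 77.2%
- 10% extra, n = 25.2: 75.5%
- 20% extra, n = 22.4: 71.8%
- 30% extra, n = 19.6: 67.6%

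These figures are the same whether the patient was withdrawn, or kept and excluded.

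**4. Under the looser wording the paths can separate.** This is an illustration with assumed inputs. Let a fraction f of placebo patients (10% to 30%) receive off-algorithm therapy that restores g points of FVC (2.5 to 5).

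- Kept and included: expected difference = 5 − f × g, from 5 − 0.10 × 2.5 = 4.75 to 5 − 0.30 × 5 = 3.5. Power at 28 per arm is 75.6% to 56.9%.
- Withdrawn or excluded, with MAR true: the difference stays at 5. Only placebo shrinks, so SE = 9 × √(1/28 + 1/(28(1 − f))), and power is 77.1% to 72.7%.

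The two rows estimate different things: one includes the effect of the added therapy and the other does not. The illustration shows that the exclusion wording settles which is estimated. It does not measure a loss caused by the conflict.

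**The case against.** The strongest reply is that 3.1 excludes later PD data anyway, so withdrawing or keeping the patient makes no difference to the primary analysis. That is right wherever the rule in 3.1 is applied as written. It does not dispose of the conditional wording in Protocol 11.1 and SAP 4, or of the narrower scope of SAP 6.1.1. It also does not reach the supplementary analysis or the steroid endpoints.

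Other replies stand in part:

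- *Rescue medication is not defined, and 11.1 treats off-algorithm changes as changes of background therapy.* The two terms may be meant as distinct, but 6.10 makes no exception for the changes that 3.1 allows.
- *7.2 covers patients who stop treatment or choose to leave, whereas 6.10 covers an investigator's judgement.* This reduces the tension. However, 7.2 also has the investigator stop study treatment when continuing would harm the patient, and then does not treat that as study withdrawal. A similar judgement leads to withdrawal under 6.10.
- *8.4.2 gives the usual timing and 3.1 is an express exception.* This stands. Section 8.4.2 does not say that restart is confined to the period after V299, and a cross-reference would settle it.
- *Listing rescue medication in 11.3 may simply record deviations.* This stands. It is weak evidence of conflict.
- *Deviation code CMD02 in SAP Table 4-1 may catch methotrexate or azathioprine restart.* It applies to prohibited medication with a relevant effect. The prohibited-treatment table (Table 5-1) is blacked out, so this cannot be checked, and neither can whether restart forces treatment discontinuation under 7.2.
- *MAR is not the only option.* Protocol 11.4.3 and SAP 6.1.3.1 allow other assumptions, and Protocol 11.4.6 describes a penalty analysis after steroid increases. All are optional. Observed post-change FVC would inform them, and the withdrawal path does not supply it.

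**Conclusion.** The conflict between 6.10 and 3.1 holds, sharpened by 7.2 and to a lesser degree by 8.4.2. Its direct effect is on whether FVC exists for the supplementary and any non-MAR analysis, and on whether off-algorithm steroid increases enter the any-reason endpoints. The primary analysis depends on the path only where the conditional rule of Protocol 11.1 and SAP 4, or the wording of SAP 6.1.1, is applied in place of the rule in 3.1.

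A reader might infer that the conflict itself biases the primary Week 16 difference. For example, suppose 4 of 28 placebo and 1 of 28 active patients are lost, with unseen values 9 points below the MAR prediction. The difference would be understated by (4 − 1) × 9/28 = 0.96 points. Rounding this to 1, power at a difference of 4 would be Φ(4/2.405 − 1.2816) = 65% instead of 79%. The arithmetic is right, but the documents do not support the inference. The split and the shortfall are assumptions. The same departure from MAR would also arise if every site followed 3.1, because those values are then excluded. Nor can it be said that the sections are impossible to follow together while Table 5-1 cannot be seen.

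The documents give no rate of off-algorithm therapy, so no bias or power loss is attributed to the conflict. It should be corrected because it leaves data capture to a site's reading and the correction is small.

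**What to change.** 1. Reconcile Protocol 3.1, 6.10, 7.2 and 8.4.2 into one rule with cross-references, and define rescue medication so that the listing in 11.3 has a clear meaning. Which clinical rule applies is for the sponsor.
2. State one identical data-exclusion rule in Protocol 3.1 and 11.1 and in SAP 4 and 6.1.1. It should cover methotrexate or azathioprine restart as well as off-algorithm steroid increases, and say whether exclusion is conditional and whether it runs for one visit or onwards.
3. State in Protocol 7.2 and Table 8-1 that patients who change background therapy or stop study treatment, and who have not withdrawn consent, keep the scheduled spirometry through V299, because V399 has none.

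The cost is a protocol amendment and a SAP amendment. No new visits are needed, but some patients who stop treatment would attend scheduled visits that they would otherwise skip. Item 3 is not neutral: it cannot be combined with a rule that ends all participation. If the sponsor adopts such a rule, the SAP should say that these patients contribute no later FVC to the supplementary analysis and how their steroid endpoints are handled.
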